After 12 participants have completed the study (placebo N=4; lemborexant N=8), an interim analysis will be performed for efficacy to see if there is a significant difference in CSF pT181/T181 between lemborexant 25 mg and placebo groups. If there is a statistically significant ($p<0.05$) or trend towards statistically significant ($p<0.1$) reduction in the primary outcome (CSF pT181/T181 ratio) or secondary outcome (CSF amyloid-beta), then the study may be continued at lemborexant 25 mg. If there is not a trend towards a statistically significant ($p>0.1$) reduction in the primary outcome (CSF pT181/T181 ratio) or secondary outcome (CSF amyloid-beta), or power analysis suggests that statistical significance will not be achieved by the fully enrolled study, then the study will be terminated.

3.5 Data Analysis Plan:

For each participant, AD biomarkers (A β 38, A β 40, A β 42, T181, S202, T217, pT181, pS202, pT217) will be normalized to the average of the first 6 hours ($t=0-6$, 20:00-02:00) before changes from the intervention will be seen in CSF. We will also normalize to the hour 0 concentration. Phosphorylated tau ratios (pT181/T181, pS202/S202, pT217/T217) will be normalized to the first time point (hour 0). The trajectory of changes from these baselines over time will then be plotted by treatment arms to examine whether the change in concentrations or ratios is linear. If the linearity assumption is valid, (linear mixed effects) LME models with random intercept and slope, similar to our previous work^{3, 5}, will be used for analysis, otherwise mixed model for repeated measure (MMRM) will be used. Fixed effect in the model will include treatment group, time and their interaction. Baseline will be included as a covariate. The normality assumption will be examined using residual plot and appropriate transformation (e.g., log) will be considered. Unstructured covariance matrix will be used and if there is convergence issue, various other covariance matrix structure (e.g., compound symmetry, First-order Autoregressive) will be compared and the best fit structure will be selected for final analysis based on Akaike information criterion (AIC).

Lemborexant 25 mg Overview
[name], Washington University

3.6 Study Outline and Timeline:

[figure not shown]

Figure 6 shows an overview of the study design with a habitual bedtime of 22:00. Table 5 shows the study timeline. We anticipate that this study will take 2 years to complete.

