- Pittsburgh Sleep Quality Index >5

7.3.2 Exclusion criteria:

- Cognitive impairment as determined by history of MMSE < 27
- Inability to speak or understand English
- Any sleep disorders other than insomnia
 - No history of moderate-to-severe sleep-disordered breathing and STOP-Bang score > 5
 - History or reported symptoms suggestive of restless legs syndrome, narcolepsy or other sleep disorders
 - No more than mild sleep apnea (AHI <16) on PSG
- Sleep schedule outside the range of bedtime 22:00-midnight
- Contraindication to lumbar catheter (anticoagulants; bleeding disorder; allergy to lidocaine or disinfectant; prior central nervous system or lower back surgery)
- Cardiovascular disease requiring medication except for controlled hypertension (PI discretion)
- Stroke
- Hepatic or renal impairment

Lemborexant 25 mg Overview
[name], Washington University

- Pulmonary disease (PI discretion)
- Type 1 diabetes
- HIV or AIDS
- Neurologic or psychiatric disorder requiring medication (PI discretion)
- Suicidal ideations
- Alcohol, tobacco or marijuana use (PI discretion)
- Use of sedating medications (PI discretion)
- Inability to get out of bed independently
- In the opinion of the investigator, the participant should be excluded due to an abnormal physical examination.
- Current pregnancy
- Body Mass Index >35
- History of migraines (PI discretion)
- History of drug abuse in the last 6 months
- History or presence of any clinically significant medical condition, behavioral or psychiatric disorder (including suicidal ideation), or surgical history based on medical record or patient report that could affect the safety of the subject or interfere with study assessments or in the judgment of the PI participant is not a good candidate.
- Urinary or fecal incontinence
- Concurrently enrolled in another trial of an investigational drug or device

We will enroll up to 30 participants to complete the study. **Participants will receive either placebo or lemborexant 25 mg, a dual orexin receptor antagonist. Lemborexant is approved by the Food and Drug Administration (FDA) for the treatment of insomnia (approved doses 5-10 mg).** Lemborexant 25 mg will be used in this study to see if there is an effect on CSF pT181/T181 and A β . The use in this study will be considered investigational and is not approved by the Food and Drug Administration (FDA).

Participants that screen fail may be invited back to rescreen at a later date.

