Sampling plan and justification:

- Power calculations are shown in “C3. Power Calculation” portion of the research plan above. Due to concerns about recruitment if participants have to repeat the study, the study power calculation is based on each participant completing the study once without repeating.
- Children will be excluded and age range will be limited to 60-80, as detailed in the previous section “Subject population characteristics”.

Vulnerable populations: We will not enroll participants from vulnerable populations.

Assignment to a study group: Participants will be randomized to receive placebo or lemborexant 25 mg at the Clinical Translational Research Unit (CTRU) admission. We will randomize 8 participants to receive 25 mg of lemborexant for 2 nights and 4 participants to receive placebo for two nights. After an interim analysis for safety and futility, a decision will be made to either: 1) continue the study with lemborexant 25 mg, 2) continue the study

Eisai Inc.

Version 3.0 2023-06-08

CONFIDENTIAL

Page 22 of 58

Lemborexant 25 mg Overview

[name], Washington University

with a lower dose of lemborexant, or 3) stop the study. If the study is continued, then 12 participants will be randomized to lemborexant and 6 participants will be randomized to placebo. In addition to being a FDA approved drug for the treatment of insomnia, lemborexant is also a drug with the same mechanism of action as was used in experiments to decrease A β with sleep in mice, therefore this will be a direct translation of this finding. The drug's mechanism of action is to block orexin-A and orexin-B receptors. The orexin neuropeptide acts in the brain to promote wakefulness. Through antagonism of this system, sleep is induced.

Collaborating sites: None

7.4 Description of Study Visits:

At all study visits, safety assessments will consist of monitoring and recording all adverse events (AEs) at each visit.

7.4.1 Visit 1:

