This study is a clinical trial, however it is not an NIH-defined phase III clinical trial. Lemborexant is FDA-approved for the treatment of insomnia. This study will use lemborexant 25 mg, which is higher than the FDA approved dose. Comparisons are being made between poorly-sleeping older adults treated (lemborexant) and untreated individuals (placebo). There is a Data Safety Monitoring Committee and monitoring plan as described in section “*2.B Protections Against Risk*” above. In compliance with the Washington University School of Medicine Institutional Data Safety Monitoring (DSM) Plan. The PI, research coordinator and members of the research team will review all study data as it becomes available. Investigators not involved with the study will independently review the safety data after 5 participants have completed the study and state if the study should be continued or not. The report will include the protocol title, IRB protocol number, IND number, the activation date of the study, the number of subjects enrolled to date, the date of first and most recent subject enrollment, a summary of all adverse events regardless of severity or relationship to subject dropouts and corresponding reason for dropout, the investigational plan for the coming year, any new information related to the investigational drug or a summary of any recent literature that may affect the safety and ethics of the study.

Given that the study requires significant involvement from the participants, we have taken steps to make the study less taxing for participants. These steps include having nurses available in the CTRU for assisting the research participants at all times and providing 24 hour/7 day/week access to study staff and physicians.

All participants will be identified by a de-identified study number to protect patient confidentiality. Participants may be linked to the “Lemborexant Sleep” study in Epic if they already have a record in the Epic system. Spreadsheets listing the participants’ name and corresponding study number will be managed by the study coordinator, and will be stored in a password protected file behind the Neurology firewall. Only the research team will have

Eisai Inc.

Version 3.0 2023-06-08

CONFIDENTIAL

Page 43 of 58

Lemborexant 25 mg Overview
[name], Washington University

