access to this spreadsheet. Data monitoring and analysis will be performed by the principle investigator. Data will also be collected on any adverse events related to the study procedures.

All data from mass spectrometry analyses are electronically uploaded and locked in the [name] laboratory's database (Firebird 2.1.4) blinded to clinical status and other variables. Future studies may involve a collaboration with [name], an A β stable isotope labeling kinetics (SILK) expert in modeling at Washington University, the A β SILK data will be analyzed with the compartmental model using the SAAM II modeling program blinded to clinical status and other variables. All statistical analyses will be conducted in collaboration with [name], an expert in statistics at Washington University, or the ICTS biostatistics core. All data is compared in a pre-specified fashion.

17. ClinicalTrials.gov Requirements

This study will be registered at ClinicalTrials.gov and the final study results will be reported on the website within 12 months of study completion. This will enable registration of primary and secondary aims and allow for broadest publication in journals.

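### The investigator is assigned monitoring and analysis, nobody independent is named to run or receive the interim efficacy comparison, and the primary model is chosen from plots by arm

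*Combined protocol and SAP*

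**What the plan says.** **Who analyses and who sees data.** Section 16 states "Data monitoring and analysis will be performed by the principle investigator" and "The PI, research coordinator and members of the research team will review all study data as it becomes available". Section 12.10 repeats the second statement. Neither says whether the data reviewed are pooled or carry arm labels. Section 16 also says that statistical analyses are done jointly with a statistician or the ICTS biostatistics core, that comparisons are pre-specified, and that mass spectrometry data are locked blinded.

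**The interim.** Section 3.4 places it after 12 completers, 8 on lemborexant and 4 on placebo, and gives its purpose: "interim analysis will be performed for efficacy to see if there is a significant difference in CSF pT181/T181 between lemborexant 25 mg and placebo". If the criterion is met on pT181/T181 or on amyloid-beta, "then the study may be continued at lemborexant 25 mg"; otherwise the study is terminated. The assignment paragraph in Section 7.3 describes it differently: "After an interim analysis for safety and futility, a decision will be made to either" continue at 25 mg, continue at a lower dose, or stop. Neither section names the analyst, the recipient or the decision-maker.

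**The model.** Under Section 3.5 the changes from baseline "will then be plotted by treatment arms to examine whether the change in concentrations or ratios is linear". That inspection decides between a linear mixed-effects model and an MMRM.

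**Other roles.** Section 7.3.2 marks six exclusions as at the investigator's discretion and adds two that rest on the investigator's judgement. The investigator approves discharge (Section 10.5). Adverse event severity and causality are graded by the investigator or a designee (Section 11.8).

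**Outside review.** The DSMC discusses safety forms, with meetings given by way of example at 5, 10 and 15 completers (Section 13.2). Outside investigators review safety data (Sections 12.10 and 16).

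**The concern.** The plan gives one role both the analysis and discretionary decisions about the trial, and places an efficacy comparison by arm well before enrolment ends. Nothing in the available text keeps that comparison from the investigator. Three steps are then open to influence by a known result: a continuation decision worded as permission rather than as a rule, the choice of primary model, and the way discretionary eligibility criteria are applied to later participants. In a trial of at most 30 people, a reader of the final report could not rule out that the first two followed the observed difference. That is a loss of credibility which wording could prevent.

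**Working it through.** **1. How much of the trial follows the interim.** Inputs: 8 + 4 before the interim (Sections 3.4 and 7.3), and 12 + 6 after it if the study continues (Section 7.3).
- Total: (8 + 4) + (12 + 6) = 12 + 18 = 30. Arms: 8 + 12 = 20 and 4 + 6 = 10. Both agree with Section 3.3.
- Share after the interim: 18/30 = 60%. This is an upper limit, because 30 is a maximum and the study may stop.

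**2. Who could stand between the investigator and arm-level results.**

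| Safeguard | Where | What it covers |
|---|---|---|
| Blinded mass spectrometry | Section 16 | The assay value |
| Statistician or biostatistics core | Section 16 | Joint analysis; not described as independent or as holder of the codes |
| Outside investigators | Sections 12.10, 16 | Safety data |
| DSMC | Section 13.2 | Safety forms; no interim or efficacy role |

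None limits who sees the interim comparison by arm.

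**3. Does interim knowledge reach later allocations?** Participants are screened at Visits 1 to 3 and randomised at admission to the research unit (Sections 7.3 and 7.4). Results from 12 completers do not show what a later participant will receive. A shift in discretionary eligibility would therefore act on both arms. It changes who is studied, and it would bias the comparison only if coming assignments could be predicted, which the documents do not indicate.

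**4. How informative is continuing in itself?** This shows what remains even if arm-level results are withheld.
- Planning effect from Table 4: d = (1.56 + 1.09)/√[(1.41² + 2.20²)/2] = 2.65/1.848 = 1.434, against 1.43 stated. The noncentral t gives power of 85.6% at 10 per group, against 86% stated.
- At 8 vs 4: noncentrality = 1.43 × √(8 × 4/12) = 2.34, with 10 degrees of freedom. The chance of two-sided p<0.1 on pT181/T181 alone is about 70% (p<0.05: about 56%).
- With no effect, a reduction at two-sided p<0.1 has probability 0.05 per outcome. For two outcomes, 1 − 0.95² = 9.75%.

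Assumptions: lemborexant has the suvorexant 20 mg effect, there is a single amyloid-beta measure independent of pT181/T181, and the test is the two-sample t test of Section 3.3. Section 3.4 names no test. On these terms a decision to continue signals a favourable interim.

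**5. The model step.** Section 16 calls the comparisons pre-specified, but Section 3.5 settles the model form after a view of the results by arm. The two statements do not fit together for this step.

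**The case against.** The strongest reply has four parts.

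*The sentences in Section 16 are read too hard.* The one on analysis closes a paragraph about identifiers and adverse event data, and the next paragraph brings in a statistician. The one on team review reads as institutional monitoring-plan wording. This stands in part. A reader might infer that the investigator analyses alone, or that arm-level results go to the whole team; the documents say neither. But collaboration is not a barrier, and no other sentence supplies one.

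*Interim knowledge does not unblind the trial.* This stands. A reader might infer that the remaining 60% are selected or graded with knowledge of their arm. Randomisation at admission means that they are not. A reader might also infer that recognising four placebo trajectories comes close to unblinding individuals. Those participants have finished dosing and sampling, and at most the rest of their 28-day adverse event period (Section 13.2) is open. Grading may also be done by a designee, and the DSMC discusses the forms.

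*Choosing a model from plots by arm is a fault whoever does it, with or without an interim.* True. It belongs here because the same control over arm labels removes it, not because the interim causes it.

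*A masking statement may exist elsewhere.* The available pages do not say who is masked in this trial, and some pages were not available. The point does not need that absence: masked tablets would not keep an interim comparison by arm from the person who runs it.

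**Conclusion.** The concern holds as a statement of what the plan permits. The investigator may see arm-level efficacy results with up to 18 of 30 participants (60%) still to be enrolled, and the primary model is chosen after inspection by arm. The exposure is confined to the continuation decision, the choice of model and possible drift in case mix. Measurement of the primary outcome is protected by blinded mass spectrometry, and later allocations are not revealed. The documents give no basis for estimating a bias, and no stated sample size, power or alpha changes. This is a correctable weakness that should be fixed, not a fatal one. The conclusion assumes that the unavailable pages contain no rule restricting arm-level access.

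**What to change.** Amend Sections 3.4, 3.5 and 16 as follows.

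1. The collaborating statistician or the ICTS biostatistics core holds the allocation codes and runs the interim comparison.
2. Results by arm go only to the existing DSMC. Section 13.2 extends its remit to this one review at 12 completers, which falls between the meetings given as examples at 10 and 15.
3. The investigator receives only the recommendation. Sections 3.4 and 7.3 must first be reconciled on the interim's purpose (efficacy, or safety and futility) and on the options open afterwards.
4. Ongoing review by the team uses data without arm labels.
5. The primary model is fixed before any arm-level look, and so before the interim. It is either pre-specified outright, or linearity is judged on individual trajectories without arm labels.

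**Cost.** Mainly protocol wording, using people already named. The DSMC takes on a small additional task, and its described expertise does not mention statistics, so the statistician would need to present the results. The investigator waits for arm-level results. Unlabelled or pooled plots may miss non-linearity confined to one arm, which favours pre-specifying the model. The protection is partial, since a recommendation to continue still signals that the interim criterion was met.

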18. APPENDICES

18.1 Appendix 1: Lemborexant 25 mg Safety Data

Introduction

Lemborexant (LEM) is a dual orexin receptor antagonist approved in the US, Japan, Canada, Australia, and other Asian countries for the treatment of adult patients with insomnia. Doses of 2.5 (LEM 2.5; Japan only), 5 mg (LEM5) and 10 mg (LEM10) are currently approved for these patients. Across the clinical program, a total of 150 subjects in 7 studies were exposed to lemborexant (E2006) 25 mg (LEM25). Multiple doses of LEM25 were evaluated in three multiple dose studies, E2006-A001-002, E2006-A001-003, and E2006-G000-201, which are described in more detail below. Other studies not included in this overview employed single dose paradigms.

Study E2006-A001-002 (NCT01673451)

Study Design

This was a single-center, randomized, double-blind, placebo-controlled, sequential, multiple-dose study. The study was conducted in 2 parts: Part A (6 cohorts of healthy adults receiving evening dosing) and Part B (1 cohort of elderly adults receiving evening dosing).

In Part A, it was planned for a total of 48 healthy adult subjects (18 to 55 years) to be enrolled into 1 of 6 cohorts sequentially in a gradual dose escalation manner, randomized to receive either LEM or matching placebo in the evening 30 minutes before habitual bedtime, and after 3 hours fasting, each night for 14 days. Each cohort was comprised of 6 LEM- and 2 placebo-treated subjects. Blood samples were collected for PK analysis at prespecified timepoints, and PD assessments were conducted (not reported here).

During Part B, one cohort of 8 elderly subjects (≥ 65 to 80 years) were randomized and treated for 14 days in the evening with LEM25 or matching placebo 30 minutes before habitual bedtime, and after 3 hours fasting. This cohort comprised 6 LEM- and 2 placebo-treated subjects. Blood samples were collected at prespecified timepoints, and PD assessments were conducted.

Overall, 55 subjects were randomized, and all received study drug (placebo, lemborexant 2.5 mg, 5 mg, 10 mg, 25 mg, 50 mg, 75 mg). A total of 11 subjects (6 adult, 5 elderly) were randomized to LEM25.

Summary of Adverse Events

There appeared to be more treatment-related TEAEs with increasing doses of LEM, and the overall incidence of TEAEs was higher in LEM (all doses) (92.7%) compared to placebo (78.6%). There were no serious TEAEs. In the LEM groups, 1 subject (2.4%) in the LEM25 group had a TEAE leading to study drug dose adjustment and withdrawal from the study.

Lemborexant 25 mg Overview
[name], Washington University

This subject discontinued study drug due to an AE (pyrexia) that was not considered to be related to study drug and was withdrawn from the study (Table 1).

Table 1 Overview of Treatment-Emergent Adverse Events – Safety Analysis Set, Study E2006-A001-002

Category	Placebo (N=14)	E2006							E2006 Total (N=41)
		2.5mg (N=6)	5mg (N=6)	10mg (N=6)	25mg (N=6)	25mg Elderly (N=5)	50mg (N=6)	75mg (N=6)	
TEAEs	11 (78.6)	5 (83.3)	5 (83.3)	6 (100)	5 (83.3)	5 (100)	6 (100)	6 (100)	38 (92.7)
Treatment-related TEAEs^a	6 (42.9)	3 (50.0)	3 (50.0)	4 (66.7)	4 (66.7)	5 (100)	6 (100)	6 (100)	31 (75.6)
Severe TEAEs	0	0	0	0	0	0	0	0	0
Serious TEAEs	0	0	0	0	0	0	0	0	0
Deaths	0	0	0	0	0	0	0	0	0
Other SAEs	0	0	0	0	0	0	0	0	0
Life Threatening	0	0	0	0	0	0	0	0	0
Requires inpatient hospitalization or prolongation of existing hospitalization	0	0	0	0	0	0	0	0	0
Persistent or significant disability or incapacity	0	0	0	0	0	0	0	0	0
Congenital anomaly / birth defect	0	0	0	0	0	0	0	0	0
Important medical events	0	0	0	0	0	0	0	0	0
TEAEs leading to study drug dose adjustment	0	0	0	0	1 (16.7)	0	0	0	1 (2.4)
TEAEs leading to study treatment withdrawal	0	0	0	0	1 (16.7)	0	0	0	1 (2.4)

Table 1 Overview of Treatment-Emergent Adverse Events – Safety Analysis Set, Study E2006-A001-002

Category	Placebo (N=14)	E2006							E2006 Total (N=41)
		2.5mg (N=6)	5mg (N=6)	10mg (N=6)	25mg (N=6)	25mg Elderly (N=5)	50mg (N=6)	75mg (N=6)	

Placebo group includes placebo subjects pooled from all cohorts in the study. Percentages are based on the total number of subjects in relevant treatment group.

For each row category, a subject with 2 or more adverse events in that category is counted only once. MedDRA = Medical Dictionary for Regulatory Activities; TEAE = treatment-emergent adverse event, SAE = serious adverse event.

a: Includes TEAEs considered by the investigator to be possibly or probably related to study drug or TEAEs with missing causality. MedDRA Version 16.0.

Source: [Table 14.3.1.2](#).

Serious Adverse Events – Safety Analysis Set

No TEAEs in any treatment group were severe. The adult LEM groups that reported only mild TEAEs were 2.5, 5, 10, and 25 mg. In the elderly LEM25 group, there was one TEAE of somnolence and one TEAE of hypoxia, both of which were rated moderate.

Overall Safety Conclusions

LEM was safe and well-tolerated following dosing in adult subjects up to 75 mg per day for 14 days, and in elderly subjects receiving 25 mg per day for 14 days. There was a higher incidence of treatment-related TEAEs among LEM subjects (all doses) (31/41, 75.6%) compared to placebo subjects (6/14, 42.9%). The incidence of treatment-related TEAEs appeared to be dose-related with higher rates occurring at higher doses, the highest incidence (100%) occurring in the LEM25 elderly, LEM50, and LEM75 dose groups. However, most TEAEs were mild in severity. No SAEs were reported during the study.

Study E2006-A001-003 (NCT02039089)

Study Design

This was a single-center, multiple-dose, randomized, double-blind, placebo-controlled, parallel-group study in healthy male and female subjects. The study consisted of 2 parts: Part A (3 cohorts of healthy Japanese subjects dosed in the evening) and Part B (1 cohort of healthy white subjects dosed in the evening). The cohorts were conducted sequentially. Part A was started first with the 2.5-mg dose cohort, followed by the 10-mg dose cohort, and then the 25-mg dose cohort. Part B was conducted in parallel with the 10-mg cohort of Part A, with overlap. Subjects received treatment with study drug for 14 days.

Summary of Adverse Events

The number of subjects with TEAEs and the incidence of TEAEs were low and similar across dose groups. No trends with dose or race were seen. Most TEAEs were judged by the investigator to be treatment related (i.e., related or not related as described in the clinical study protocol to study drug). All TEAEs were mild. There were no severe TEAEs, serious TEAEs, TEAEs leading to withdrawal, or deaths during the study. All TEAEs resolved by the end of the study.

Somnolence and abnormal dreams were the most frequently reported treatment-related TEAEs, with 4 Japanese subjects (1 each in the placebo and 2.5-mg groups, and 2 in the 25-mg group) and 1 white subject (10-mg group) reporting somnolence and 1 Japanese subject (25-mg group) and 2 white subjects (10-mg group) reporting abnormal dreams (Table 2).

Table 2 Summary of Treatment-emergent Adverse Events (Safety Analysis Set, Study E2006-A001-003)

Characteristic	Japanese					White		
	Placebo N = 6 n (%) E	2.5 mg N = 6 n (%) E	10 mg N = 6 n (%) E	25 mg N = 6 n (%) E	Overall Japanese N = 18 n (%) E	Placebo N = 2 n (%) E	10 mg N = 6 n (%) E	
TEAEs	2 (33.3%) 3	1 (16.7%) 2	0	2 (33.3%) 4	3 (16.7%) 6	1 (50.0%) 1	3 (50.0%) 3	
Serious TEAEs	0	—0	0	0	0	0	0	
Severe TEAEs	0	0	0	0	0	0	0	
Related TEAEs	2 (33.3%) 2	1 (16.7%) 2	0	2 (33.3%) 3	3 (16.7%) 5	0	3 (50.0%) 3	
TEAEs Leading to Withdrawal	0	0	0	0	0	0	0	
TEAEs Leading to Death	0	0	0	0	0	0	0	

Overall Safety Conclusions – Study 003

Multiple ascending doses of LEM were safe and well tolerated in healthy Japanese and white subjects in this study. The incidence of TEAEs were low and similar across dose groups, and the most common TEAE was somnolence. There were no significant patterns in laboratory parameters to suggest a relationship to dose group. No TEAEs were related to laboratory or hematology measurements. Urinalysis test results were mostly negative or normal; no abnormal test results were considered to be of clinical significance. Vital signs, ECG parameters, and high-precision QT analyses were unremarkable, and an effect on the placebo-corrected change-from-baseline QTcI ($\Delta\Delta\text{QTcI}$) exceeding 10 msec could be excluded at the observed peak plasma level after multiple dosing up to 25 mg/day for 14 days.

Study E2006-G000-201 (NCT01995838)

Study Design

E2006-G000-201 was a multicenter, multiple dose, randomized, double-blind, placebo-controlled, parallel-group, Bayesian adaptive, dose-response study in subjects with chronic insomnia. Subjects were randomized to 1 of 6 doses of LEM (1 mg, 2.5 mg, 5 mg, 10 mg, 15 mg, or 25 mg) or placebo according to the randomization scheme.

The study had 2 phases: Prerandomization and Randomization. The Prerandomization Phase lasted up to 21 days and consisted of a Screening Period (Days –21 to –2) and a Baseline Period (Day –1). After the Baseline Period, all eligible subjects were randomized in a double-blind manner to receive LEM or placebo for 15 nights during the Treatment Period (Days 1 to 15). All subjects then received placebo in a single-blind manner, for 2 nights (Days 16 to 17) during the Rebound Insomnia Assessment Period (Days 16 to 18). Subjects did not receive study drug during the Follow-up Period (Days 19 to 30).

Summary of Adverse Events

